7.3 Method of Treatment Assignment

Treatment allocation/randomization will occur centrally using an interactive voice response system / integrated web response system (IVRS/IWRS). There are 2 study treatment arms. Participants will be assigned randomly in a 1:1 ratio to pembrolizumab + epacadostat or pembrolizumab + epacadostat matching placebo.

7.3.1 Stratification

Treatment allocation/randomization will be stratified according to the following factors:

1. Bajorin risk score; based on the presence of visceral (lung, liver, or bone) metastasis and/or KPS <80%.
 - a. 0 (neither criterion)
 - b. 1 (exactly 1 criterion)
 - c. 2 (both criterion)
2. PD-L1 Expression
 - d. CPS \geq 10 per IHC assay
 - e. CPS <10 per IHC assay

7.4 Blinding

A double-blinding technique with in-house blinding will be used. Epacadostat and matching placebo will be packaged identically so that the blind is maintained. The participant, the investigator, the Sponsor, MSD study personnel, or delegate(s) who are involved in the study treatment administration or clinical evaluation of the participants are unaware of the group assignments.

NOTE: As of Amendment 04, the study will be unblinded after the last participant completes Week 9 imaging assessment for efficacy analysis. After unblinding, for participants who are benefiting from study treatment and upon discussion with the investigator, the participant, study site personnel, Sponsor, and MSD or designee will be informed of the study treatment they receive (eg, pembrolizumab, or pembrolizumab in combination with epacadostat).

Pembrolizumab, which will be dosed to all participants in both treatment arms, will not be blinded.

See Section 9.1.11 for a description of the method of unblinding a participant during the trial, should such action be warranted.

7.5 Preparation/Handling/Storage/Accountability

7.5.1 Dose Preparation

Details on preparation and administration of IV pembrolizumab are provided in the Pharmacy Manual. Epacadostat and matching placebo are oral tablets and do not require preparation.

For epacadostat in such cases where a participant is unable to swallow tablets or has a feeding tube instruction for dose crushing, administration and dose preparation are detailed in the Pharmacy Manual. In addition written guidance for safe handling of the epacadostat tablets will be provided to the participant/caregivers.

7.5.2 Handling, Storage and Accountability

The investigator or designee must confirm appropriate temperature conditions have been maintained during transit for all study treatment received and any discrepancies are reported and resolved before use of the study treatment.

Only participants enrolled in the study may receive study treatment and only authorized site staff may supply or administer study treatment. All study treatments must be stored in a secure, environmentally controlled, and monitored (manual or automated) area in accordance with the labeled storage conditions with access limited to the investigator and authorized site staff.

The investigator, institution, or the head of the medical institution (where applicable) is responsible for study treatment accountability, reconciliation, and record maintenance (ie, receipt, reconciliation, and final disposition records).

For all trial sites, the local country MSD personnel or designee will provide appropriate documentation that must be completed for drug accountability and return, or local discard and destruction if appropriate. Where local discard and destruction is appropriate, the investigator is responsible for ensuring that a local discard/destruction procedure is documented.

The trial site is responsible for recording the lot number, manufacturer, and expiry date for any locally purchased product as per local guidelines unless otherwise instructed by MSD.

The investigator shall take responsibility for and shall take all steps to maintain appropriate records and ensure appropriate supply, storage, handling, distribution and usage of study treatments in accordance with the protocol and any applicable laws and regulations.

7.6 Treatment Compliance

Interruptions from the protocol-specified treatment plan for greater than 12 weeks from the last dose require consultation between the Investigator and MSD and written documentation of the collaborative decision on participant management.

7.6.1 Administration and Compliance of Pembrolizumab

Administration of IV pembrolizumab will be witnessed by the Investigator and/or study staff. The total volume of study treatment infused will be compared with the total volume prepared to determine compliance with each dose administered. Pembrolizumab will be administered on an outpatient basis.

Instructions for preparing and administering pembrolizumab are provided in the Pharmacy Manual.

7.6.2 Administration and Compliance of Epacadostat or Matching Placebo

Participants will take their dose of epacadostat or matching placebo in the morning and evening, approximately 12 hours apart without regard to food. If the morning or evening dose is missed by more than 4 hours, that dose should be skipped and the next scheduled dose should be taken at the usual time. If the participant vomits after taking a tablet, the dose should not be re-administered until the next scheduled dose. Participants will self-administer epacadostat or matching placebo except on Cycle 1 Day 1 (C1D1), and Cycle 2 Day 1 (C2D1), when the morning dose will be given at the study site clinic prior to the pembrolizumab infusion.

Participants will be instructed to bring all study treatments with them to the study visits in order for site personnel to conduct tablet counts to assess study treatment accountability. Investigators and their staff should evaluate compliance at each visit, and take appropriate steps to optimize compliance.

7.7 Concomitant Therapy

7.7.1 Acceptable Concomitant Medications

All treatments that the investigator considers necessary for a participant's welfare may be administered or changed at the discretion of the investigator in keeping with the community standards of medical care and prohibited medications in this study. All concomitant medication will be recorded on the case report form (CRF) including all prescription, over-the-counter, herbal supplements, and IV medications and fluids. If changes occur during the study period, documentation of drug dosage frequency, route, and date will also be included on the CRF.

Palliative and supportive care is permitted during the course of the study for underlying medical conditions and management of symptoms. Surgery for tumor control is not permitted during the study. Palliative radiotherapy is permitted to a limited number of lesions if considered medically necessary by the treating physician as long as the lesions are NOT a RECIST 1.1-defined target lesion. Study treatment should be held during the course of palliative radiotherapy and should be resumed no earlier than the next scheduled

administration of study treatment. The specifics of the radiation treatment, including the location, will be recorded.

All concomitant medications received within 28 days before the first dose of study treatment through the Safety Follow-up Visit should be recorded. After the Safety Follow-up Visit, record all medications taken for SAEs and ECIs as defined in Section 9.3. If a participant enters into second course therapy, all concomitant medications received within 30 days before the first dose of second course treatment should be recorded. Following second course therapy Safety Follow-up Visit, record all medications taken for SAEs and ECIs as defined in Section 9.3.

7.7.2 Prohibited Concomitant Medications

Medications or vaccinations specifically prohibited in the exclusion criteria are not allowed during the ongoing study. If there is a clinical indication for any medication or vaccination specifically prohibited, discontinuation from trial therapy or vaccination may be required. The investigator should discuss any questions regarding this with the MSD Clinical Director. The final decision on any supportive therapy or vaccination rests with the investigator and/or the participant's primary physician. However, the decision to continue the participant on study treatment requires the mutual agreement of the investigator, MSD, and the participant.

Study participants who must begin treatment with a medication prohibited for concomitant use with epacadostat may be treated as clinically indicated; however, treatment with epacadostat (or placebo) must be discontinued. Examples of such medications include MAO inhibitors, and UGT1A9 inhibitors. Participants may continue on treatment with pembrolizumab after consultation with MSD.

Listed below are specific restrictions for concomitant therapy or vaccination:

Participants are **prohibited** from receiving the following therapies during the Screening, Treatment, and Second Course Phases of this study:

1. Investigational agents other than pembrolizumab and epacadostat.
2. Anti-cancer medications, including chemotherapy or biologic therapy other than the study treatments.
3. Immunotherapy not specified in this protocol.
4. Prolonged therapy with systemic glucocorticoids (>7 days) for any purpose other than to modulate symptoms from an AE, SAE, or event of clinical interest (ECI) or for use as a pre-medication for chemotherapy or in participants with a known history of an IV contrast allergy administered as part of computed tomography (CT) radiography. Brief, limited use of systemic corticosteroids (≤ 7 days) are permitted where such use is considered standard of care (eg, for COPD exacerbation).

Replacement doses of steroids (for example, prednisone 5 to 7.5 mg daily) are permitted while on study, as is the use of local steroids.

5. Radiation therapy or surgery.

Note: Radiation therapy or surgery to a symptomatic solitary lesion is allowed. No pembrolizumab infusions are permitted during radiation therapy or procedure and epacadostat or matching placebo should be stopped the day treatment begins. Study treatment may be resumed as early as 1 week after treatment if the participant's symptoms are improving and not requiring corticosteroids for management. MSD consultation is required for study treatment restart after radiation therapy or surgery. If study treatment is not resumed within 12 weeks of completing treatment (radiation therapy or surgery), the participant should discontinue study treatment permanently.

6. Live attenuated vaccine within 30 days before the first dose of study treatment and while participating in the study.

- Examples of live vaccines include, but are not limited to, the following: measles, mumps, rubella, chicken pox, yellow fever, rabies, BCG, and typhoid vaccine. Seasonal influenza vaccines for injection are generally killed virus vaccines and are allowed; however, intranasal influenza vaccines are live attenuated vaccines and are not allowed.

7. Any MAOI or drug associated with significant MAO inhibitory activity agents is prohibited from 21 days before starting study treatment through 2 weeks after the final dose of epacadostat or matching placebo has been taken.

- Including, but not limited to, hydrazines (example phenelzine), meperidine, caroxazone, linezolid, echinopsidine methylene blue, furazolidon, tranlycypromine, brofaromine, metralindole, minaprine, moclobemide, pirlindole, toloxatone, lazbeimide, pargyline, rasagiline, selegiline.

8. Any UGT1A9 inhibitor, including: acitretin, amitriptyline, androsterone, cyclosporine, dasatinib, diclofenac, diflunisal, efavirenz, erlotinib, flutamide, gefitinib, gemfibrozil, glycyrrhetic acid, glycyrrhizin, imatinib, imipramine, ketoconazole, linoleic acid supplements, mycophenolic acid, niflumic acid, nilotinib, phenobarbital, phenylbutazone, phenytoin, probenecid, quinidine, ritonavir, sorafenib, sulfinpyrazone, valproic acid, and verapamil.

Participants who, in the assessment of the Investigator, require the use of any of the aforementioned treatments for clinical management should be removed from the trial.

All treatments that the Investigator considers necessary for a participant's welfare may be administered at the discretion of the Investigator in keeping with the community standards of medical care. All concomitant medication will be recorded on the eCRF including all prescription, over-the-counter (OTC) products, herbal supplements, and IV medications and fluids. If changes occur during the trial period, documentation of drug dosage, frequency, route, and date should also be included on the eCRF.

All concomitant medications received within 28 days prior to the first dose of trial treatment and up to 30 days after the last dose of trial treatment should be recorded. Concomitant medications administered 30 days after the last dose of trial treatment should be recorded for SAEs and ECIs as defined in Section 9.3.7

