8.1 Discontinuation of Study Treatment

Discontinuation of study treatment does not represent withdrawal from the study.

As certain data on clinical events beyond study treatment discontinuation may be important to the study, they must be collected through the participant's last scheduled follow-up, even if the participant has discontinued study treatment. Therefore, all participants who discontinue study treatment prior to completion of the protocol-specified treatment period will still continue to participate in the study as specified in Section 2 - SoA and Section 9.9.5 – Discontinued Participants Continuing to be Monitored in the Study.

Participants may discontinue study treatment at any time for any reason or be dropped from the study treatment at the discretion of the investigator should any untoward effect occur. In addition, a participant may be discontinued from study treatment by the investigator or MSD if study treatment is inappropriate, the trial plan is violated, or for administrative and/or other safety reasons. Specific details regarding procedures to be performed at study treatment discontinuation are provided in Section 9.1.10–Withdrawal/Discontinuation.

A participant must be discontinued from study treatment but continue to be monitored in the study for any of the following reasons:

- The participant or participant's legally acceptable representative requests to discontinue study treatment.
- The participant has a medical condition or personal circumstance which, in the opinion of the investigator and/or MSD, placed the participant at unnecessary risk from continued administration of study treatment.
- The participant has a confirmed positive serum pregnancy test.
- *Completed 35 treatment cycles (approximately 2 years) with pembrolizumab.*

Note: The number of treatments is calculated starting with the first dose. Participants who stop the combination or pembrolizumab after receiving 35 doses may be eligible for retreatment if they progress after stopping study treatment provided they meet the requirements detailed in Section 9.9.3. Participants may be retreated in the Second Course Phase (Retreatment) for up to an additional 17 cycles (approximately 1 year).

- The study is terminated by the sponsor.

- The study is terminated by the local health authority, IRB, or IEC.
- Any progression or recurrence of any malignancy, or any occurrence of another malignancy that requires active treatment.

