8.2 Withdrawal from the Study

A participant must be withdrawn from the study if the participant or participant's legally acceptable representative withdraws consent from the study.

If a participant withdraws from the study, they will no longer receive study treatment or be followed at scheduled protocol visits.

Specific details regarding procedures to be performed at the time of withdrawal from the study, are outlined in Section 9.1.10 – Withdrawal/Discontinuation. The procedures to be performed should a participant repeatedly fail to return for scheduled visits and/or if the study site is unable to contact the participant are outlined in Section 8.3.

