9.1.10 Withdrawal/Discontinuation

Participants who discontinue study treatment prior to completion of the treatment period should be encouraged to continue to be followed for all remaining study visits.

When a participant withdraws from participation in the trial, all applicable activities scheduled for the Discontinuation Visit should be performed at the time of withdrawal. Any adverse events which are present at the time of withdrawal should be followed in accordance with the safety requirements outlined in Section 9.3 - Adverse Events.

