9.2.1.3 End of Treatment and Follow-up Tumor Imaging

NOTE: As per Amendment 04, there is no protocol-specified imaging after the Week 9 assessment for efficacy analysis. This section has been updated accordingly.

For participants who discontinue study treatment before the Week 9 imaging assessment for efficacy analysis, tumor imaging should be performed at the time of treatment discontinuation (\pm 4 week window). If previous imaging was obtained within 4 weeks prior to the date of discontinuation, then imaging at treatment discontinuation is not mandatory. In participants who discontinue study treatment due to documented disease progression, this is the final required tumor imaging.

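### Section 7.7.2 gives two incompatible rules for participants who must start a MAO or UGT1A9 inhibitor, and its removal sentence matches no status defined in Section 8

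*Combined protocol and SAP*

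**What the plan says.** All of the following is current protocol text.

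- **Section 7.7.2, opening paragraphs.** For a participant who must begin a drug prohibited alongside epacadostat, "treatment with epacadostat (or placebo) must be discontinued. Examples of such medications include MAO inhibitors, and UGT1A9 inhibitors". The next sentence reads: "Participants may continue on treatment with pembrolizumab after consultation with MSD". For prohibited medication in general, the same section allows an agreed continuation: "the decision to continue the participant on study treatment requires the mutual agreement of the investigator, MSD, and the participant".
- **Section 7.7.2, after the numbered list.** Item 5 is radiation therapy or surgery, item 7 is MAO inhibitors and item 8 is UGT1A9 inhibitors. Participants who, in the investigator's view, "require the use of any of the aforementioned treatments for clinical management should be removed from the trial".
- **Section 7.7.2, note to item 5.** Radiation or surgery to a single symptomatic lesion is allowed, and study treatment may restart afterwards.
- **Section 8.1.** "Discontinuation of study treatment does not represent withdrawal from the study".
- **Section 8.2.** Withdrawal is compulsory when consent is withdrawn. "If a participant withdraws from the study, they will no longer receive study treatment or be followed at scheduled protocol visits".
- **Section 9.1.10.** When a participant withdraws, "all applicable activities scheduled for the Discontinuation Visit should be performed at the time of withdrawal".
- **Section 9.2.1.3.** If treatment stops before the Week 9 scan, "tumor imaging should be performed at the time of treatment discontinuation", within a window of 4 weeks either side. This scan is optional if imaging was done in the preceding 4 weeks.
- **Sections 10.5.1 and 10.6.1.1.** The ORR denominator is every randomized participant. The numerator is CR or PR at the first scan.

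**The concern.** A participant who newly needs a MAO or UGT1A9 inhibitor falls under both rules. Under one, pembrolizumab may go on and the Week 9 scan stays due. Under the other, the participant leaves the trial. Section 8 recognises stopping treatment and withdrawing from the study, but 7.7.2 does not say which of these removal means.

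Two things are at stake. Sites reading different sentences will treat identical participants differently. And the choice of sentence affects what response data exist: a participant removed before Week 9 may have no scan at the planned time, while still counting in the denominator of the only efficacy endpoint.

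**Working it through.** **Step 1. Compare the passages for the same participant** (already randomized, before Week 9, must start a UGT1A9 inhibitor).

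| Question | Opening of 7.7.2 | After the list in 7.7.2 |
|---|---|---|
| Epacadostat or placebo | Stops | Stops, through removal |
| Pembrolizumab | May continue after consultation | Stops, through removal |
| Status in the study | Remains | Leaves; status not defined in Section 8 |
| Week 9 scan | Due on calendar days (9.2.1.2) | Replaced at best by a discontinuation scan (9.2.1.3, 9.1.10) |

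The second and third rows cannot both be obeyed. The removal sentence also contradicts the note to item 5, because radiation and surgery are among the listed treatments and that note lets study treatment restart. Section 8.1 adds no third contradiction: it is consistent with stopping one drug and staying in the study.

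**Step 2. Can removal leave no post-baseline scan?** Baseline imaging may be up to 28 days before randomization (9.2.1.1). The 4-week waiver in 9.2.1.3 does not require the earlier image to be post-baseline. Example: baseline scan 7 days before randomization, removal on day 21. The interval is 7 + 21 = 28 days, which is 4 weeks, so the discontinuation scan is not mandatory. The case is possible but narrow. Otherwise a discontinuation scan is expected, and because 10.6.1.1 refers to the first scan, a response on it may count.

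**Step 3. Reproduce the plan's own figures.** Table 12 in Section 10.9 uses 50 per arm and Clopper-Pearson limits:

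- lower = 2.5% quantile of Beta(x, n − x + 1)
- upper = 97.5% quantile of Beta(x + 1, n − x)

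For x = 15 and n = 50: ORR 30%, limits 17.86% and 44.61%, width 26.75 points. The plan prints 17.9%, 44.6% and 26.7%. The ORR and limits of the other four rows also agree to 0.1 point.

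**Step 4. Size of the effect.** Inputs: 50 per arm (Section 10.9); a response rate of 30%, assumed from the middle of the range KEYNOTE-052 and Table 12 span; k removals per arm with no scan, assumed to be 1 to 3 because the documents give no frequency. A participant with no scan is taken to count as a non-responder. That is inferred from the ITT denominator, since Section 10 has no rule for a missing response.

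- Cost of one lost true responder: 1/50 = 2.0 points.
- Expected cost per removal without a scan: 0.30 × 2.0 = 0.6 points.
- Expected cost for k removals: 0.6 × k.

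| k | Expected loss | Worst case: all would have responded, starting from 15/50 |
|---|---|---|
| 1 | 0.6 points | 14/50 = 28% (16.2% to 42.5%) |
| 2 | 1.2 points | 13/50 = 26% (14.6% to 40.3%) |
| 3 | 1.8 points | 12/50 = 24% (13.1% to 38.2%) |

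Over the Table 12 range of 28% to 36%, the expected loss per removal is 0.56 to 0.72 points. At k = 3 and 30%, 1.8/26.75 is about 7% of the interval width.

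**The case against.** The contradiction itself is hard to dispute. The case on the other side is that little follows from it, and much of that case stands.

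- **Scans.** A reader might infer that removal before Week 9 means no response scan and an automatic non-responder. The documents do not support this. The schedule of activities, 9.1.10 and 9.2.1.3 all point to a discontinuation scan, and non-responder status is not written anywhere. The lack of a missing-response rule is a general gap in Section 10, not a product of 7.7.2.
- **Size.** A reader might multiply 2 points by 1 to 3 removals and report a loss of 2 to 6 points. That is the worst case, in which every removed participant would have responded and none was scanned.
- **Frequency.** The UGT1A9 list is long, but exclusion criterion 20 bars anyone who took a MAO or UGT1A9 inhibitor in the 21 days before treatment or expects to need one. Only unforeseen need is left. Enrollment stopped on 02-MAY-2018. If the last participant was randomized by then, Week 9 (63 days) falls by 4 July 2018, or 11 July with the 7-day window. The amendment was approved on 15 June 2018, so the period in which ORR could still be affected was short.
- **Imbalance between arms.** A reader might expect more removals in the combination arm, since Section 3.3.3 allows for more immune toxicity there. No passage directs use of a listed MAO or UGT1A9 inhibitor by name to manage toxicity, and sites are blinded until the last Week 9 scan. Imbalance is possible but not shown.
- **Safety data.** Section 9.3.1 keeps adverse event reporting in force for 90 days after treatment stops (30 days if new anticancer therapy starts), and 9.1.10 has events present at withdrawal followed. Removal does not cancel these duties, although 8.2 ends scheduled visits for anyone classed as withdrawn.

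None of this tells a site which sentence of 7.7.2 to follow.

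**Conclusion.** Wrong as written: an internal contradiction. For MAO and UGT1A9 inhibitors, 7.7.2 both permits continued pembrolizumab and calls for removal. The removal sentence also conflicts with the section's own note on radiation and surgery, and it uses a status that Section 8 does not define. The case for correcting it rests on that contradiction, not on the effect on ORR.

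The effect on ORR is probably small: about 0.6 points per removal without a scan, or 0.6 to 1.8 points for 1 to 3 per arm, beside an interval about 27 points wide in a study with no hypothesis test (Section 10.8). This assumes a 30% response rate, 50 per arm, removal before Week 9, no scan, and non-responder counting. The number of such removals is unknown.

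**What to change.** 1. Reconcile the opening paragraphs of 7.7.2 with the removal sentence after the list, and reconcile that sentence with the note to item 5. This review takes no view on which treatment rule is right.
2. Replace the removal wording with a status that Section 8 defines: treatment discontinuation or study withdrawal.
3. For MAO and UGT1A9 inhibitors, state that use of the drug alone, without withdrawal of consent, does not end study participation. The first on-study scan at Week 9 and adverse event collection under Section 9.3 then still take place, whichever treatment rule stands.
4. Do not extend statement 3 to items 2 and 3 of the list (other anti-cancer drugs and immunotherapy). Section 10 has no rule for response after new anti-cancer therapy, so a Week 9 response following such therapy could be counted towards ORR.

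The cost is protocol wording, plus a Week 9 scan for the few participants who would otherwise have only a discontinuation scan.
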